## **Setting & Participants**

The group of clinics selected reflects a purposive sample based on several criteria, including clinic size and complexity, and geography. HCV clinics were recruited via a national HCV provider email listserv and monthly HCV provider phone call. The seven HCV clinics selected were randomly assigned to either UI or AI, using set randomization, which, with small sample sizes, helps to achieve balance on a set of relevant characteristics – in this case, urban/suburban setting and on HCV patient volume.iv Two additional comparison clinics were selected purposively because they had similar patient volume, clinic complexity, and geographic locale to the other participating clinics.v Thus in total, data were collected from nine VA clinics: four AI clinics, three UI clinics, and two comparison clinics. Care teams within the HCV clinics had different compositions and involved pharmacists, nurse practitioners, registered nurses, and social worker to varying degrees.

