## **Intervention: Text Messaging for HCV treatment**

At the time of implementation, usual care for HCV included starting a patient on daily oral medication for 8-16 weeks, and follow-up in-person visits, blood lab work, and medication refills at 2- or 4-week intervals. The aTS for HCV was intended to improve processes and outcomes of care, and satisfaction with care. The HCV texting protocol included reminder text messages about medication taking, appointment keeping, and laboratory completion, and motivational text messages to encourage continued engagement in treatment. To be consistent with the standard treatment processes, each of the seven clinics worked collaboratively with study team members (VY, KM, and national aTS program office) to tailor the HCV texting protocol to align with their clinic's workflow (e.g., adjusting messaging logic from 2 to 4 weeks for different treatment intervals). Motivational messages were supportive in nature and intended to promote self-management and increase feelings of connection to the treatment team.

Message content could be tailored for content (e.g., adding clinic name and phone number) and timing (e.g., adjusting time of day that medication reminder is sent) through patient and provider discussion at the time of aTS enrollment, or later to reflect patient preferences. Veterans who did not use the aTS received otherwise standard HCV care.

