### ***Measures and Data Collection***

PRISM domains (implementation and sustainability infrastructure, intervention characteristics, recipients via both patient and organizational perspectives, external environment) guided the measures and data collection and are denoted in parentheses.

**Implementation Processes: Facilitation (Implementation and Sustainability Infrastructure).** The external facilitator (VY) logged facilitation events on a tracking sheet, including facilitation date, length of time, mode of delivery (i.e., email, phone call, or in-person visit), purpose, notes, and other observations. From the perspective of the primary facilitator, if multiple facilitation events occurred in one day, only one event per person, per day was counted.

**Implementation Outcomes: Texting Use (Intervention).** Providers logged the number of patients who were offered the aTS and noted whether patients enrolled or declined, including the reason for declining. The content of patient text message replies was extracted from the aTS portal. To be eligible for the texting protocol, patients had to be starting HCV medication treatment. There were four steps to initiate a patient on the aTS: (1) providers verbally offered patients the aTS, (2) providers registered interested patients in the aTS portal and assigned them the HCV protocol, and (3) once a patient was registered, the aTS would send an automated text message requesting the patient authenticate themselves by replying to this initial text message thus prompting the assigned HCV protocol to begin, and (4) patients actively text with the aTS.

**Clinical Effectiveness Outcomes.** Medication adherence was measured via patient text response rate, operationalized as the number of days of text-confirmed medication taking divided by the number of days

receiving medication reminder texts. Consistent with other adherence standards, an affirmative text response rate of  $\geq 80\%$  was considered high adherence.ix Clinical data, including HCV treatment regimen and duration, and lab dates and results, were extracted from VA's National HCV Dashboard with data from VA's Corporate Data Warehouse.x The goal of treatment is to achieve cure, or sustained virologic response (SVR), where there is an undetectable HCV lab result 12 weeks after completion of treatment.

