### **Data Analysis**

Descriptive and bivariate analyses of facilitation log data were conducted to compare facilitation dose, comparing UI and AI implementation groups. Descriptive and bivariate analyses were conducted on provider and patient questionnaires, text message frequencies, and clinical data to assess differences between implementation groups (UI and AI) in implementation outcomes. We then compared clinical effectiveness outcomes between texters and non-texters. We examined patient progression through the aTS initiation process, by calculating the percent retained from one step to the next, by UI and AI implementation group. Chi-square tests were used to assess differences between the two groups. All analyses were conducted in RStudio Version 1.0.153 and statistical significance was defined as  $p < 0.05$ .xxi

Qualitative interviews were audio recorded, transcribed verbatim, and then analyzed using NVivo 11 software.xxii Thematic analysis of all qualitative data (interview transcripts, meeting notes, text messages) was conducted.xxiii PRISM domains provided the deductive *a priori* codes and other codes emerged with inductive coding. The triangulation of quantitative and qualitative data served as a final step of analysis.

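### Clinics were randomised (4 AI, 3 UI), but patient retention is compared by chi-square with no allowance for clinic, so the false-positive rate probably exceeds 5%

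*Combined protocol and SAP*

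**What the plan says.** Setting & Participants makes the clinic the randomised unit: "The seven HCV clinics selected were randomly assigned to either UI or AI, using set randomization". The method was meant to balance urban or suburban setting and patient volume. The result was "four AI clinics, three UI clinics, and two comparison clinics", and the two comparison clinics were not randomised.

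Data Analysis measures progress through the texting start-up process "by calculating the percent retained from one step to the next, by UI and AI implementation group". The next sentence reads "Chi-square tests were used to assess differences between the two groups", and the threshold is p < 0.05. Other AI versus UI comparisons are described only in general terms: "Descriptive and bivariate analyses were conducted on provider and patient questionnaires, text message frequencies, and clinical data". Facilitation dose is treated in the same way.

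The document describes no clinic term, mixed model, GEE, cluster-robust variance, clinic-level summary or permutation test. It gives no patient numbers per clinic, no ICC and no sample-size calculation.

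**The concern.** A chi-square test on pooled patients is valid only if patients in the same clinic are no more alike than patients in different clinics. The plan gives three reasons to doubt that:

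- Setting & Participants: "Care teams within the HCV clinics had different compositions".
- The Intervention section, on tailoring the texting protocol: "each of the seven clinics worked collaboratively with study team members".
- Measures and Data Collection: providers make the offer, and then "providers registered interested patients in the aTS portal and assigned them the HCV protocol".

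Early-step retention is therefore partly a measure of staff behaviour, which is shared by all patients of a clinic. The implementation strategies themselves (toolkit, champion support, site visit, outreach) are also delivered to clinics.

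AI versus UI is the only comparison protected by randomisation. Texters and non-texters are self-selected, and the non-texters include patients from the non-randomised comparison clinics. With three or four clinics per arm, a few atypical clinics could produce a nominally significant strategy effect when there is none.

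**Working it through.** **Inputs from the plan.** Four versus three clinics (Setting & Participants); chi-square test at p < 0.05 (Data Analysis).

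**Assumptions, because the plan is silent.** Patients per clinic m = 10 to 50, ICC = 0.01 to 0.20, retention 0.60 in both arms. The plan does not say whether the chi-square is continuity-corrected, so both forms are shown.

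**Step 1: the plan's own figure.** With ICC = 0, the two-sided error is 2 × [1 − Φ(1.96)] = 0.050. The nominal level is right if patients are independent.

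**Step 2: clustering by formula.** The design effect is DE = 1 + (m − 1) × ICC, and the actual error is 2 × [1 − Φ(1.96/√DE)]. For m = 30 and ICC = 0.05, DE = 1 + 29 × 0.05 = 2.45, 1.96/√2.45 = 1.25, and the error is about 21%.

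**Step 3: simulation.** Beta-binomial clinics, 4 versus 3, equal sizes, no arm effect, 20,000 replicates per cell:

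| m | ICC | DE | Uncorrected | Continuity-corrected |
|---|---|---|---|---|
| 10 | 0.01 | 1.09 | 6.4% | 3.4% |
| 10 | 0.02 | 1.18 | 7.5% | 4.2% |
| 30 | 0.02 | 1.58 | 11.9% | 9.3% |
| 30 | 0.05 | 2.45 | 21.8% | 18.5% |
| 30 | 0.10 | 3.90 | 32.7% | 29.4% |
| 50 | 0.20 | 10.8 | 56.3% | 54.4% |

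Independent repeat runs agreed to within about 1 percentage point. With unequal clinics (10, 20, 40, 50 versus 10, 30, 50) and ICC 0.05, the rates were 25.3% and 21.9%.

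**Step 4: allowing for balance.** Assume four urban and three suburban clinics, split 2+2 in AI and 2+1 in UI, with setting carrying half of the between-clinic variance. At m = 30 the rates fall to 15.2% / 12.4% (ICC 0.05) and 23.0% / 20.0% (ICC 0.10). Balance reduces the excess but does not remove it.

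**Step 5: the alternative.** A t-test on the seven clinic proportions (4 + 3 − 2 = 5 degrees of freedom, critical value 2.571) held its error at 4.3% to 5.8% in every equal-size cell without the balance restriction.

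**Step 6: its precision.** SE = √[0.24 × (DE/m) × (1/4 + 1/3)], where 0.24 = 0.60 × 0.40. The difference detectable with 80% power is 3.514 × SE (noncentral t, 5 df), and the expected 95% CI half-width is 2.571 × SE.

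| m | ICC | SE | Detectable difference | CI half-width |
|---|---|---|---|---|
| 30 | 0.02 | 0.0859 | 30 points | 22 points |
| 30 | 0.05 | 0.1069 | 38 points | 27 points |
| 30 | 0.10 | 0.1349 | 47 points | 35 points |

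**Step 7: permutation limits.** Unrestricted, there are C(7,3) = 35 allocations and the smallest p is 1/35 = 0.029. If the clinics were a mix of settings and each arm's setting composition was fixed, the maximum is C(2,1) × C(5,2) = 20 for a 2/5 split (also C(6,3) = 20 for 1/6), or C(4,2) × C(3,1) = 18 for a 4/3 split. The smallest p is then 1/20 = 0.05 or 1/18 = 0.056, so p < 0.05 cannot be reached.

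**The case against.** The strongest case concerns size and severity. The documents give no patient numbers, ICC or retention rate, so every inflation figure is assumed, and the 56% comes from the most extreme cell. Denominators can only stay level or fall at later steps. At 5 per clinic and ICC 0.01 to 0.05, the error is 5.8% to 7.9% uncorrected and 2.5% to 3.6% corrected. This stands as a limit on the size. It does not remove the problem: at 5 per clinic and ICC 0.20 the rates are 16.1% and 9.1%.

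The study was classed as quality improvement, its analyses are called descriptive and bivariate, no primary outcome is named, and the quantitative results are triangulated with qualitative data. That tempers the consequences. The plan nevertheless presents a randomised comparison of effectiveness and sets a significance threshold.

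Two points of reading are weaker. The absence of clinic adjustment is inferred from silence, which is true, but the paragraph names its test, threshold and software and describes nothing else. The two groups could in principle be texters and non-texters, but the sentence directly follows the split by UI and AI.

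One point about the remedy stands. The t-test is not safe when clinic size differs strongly by arm: four AI clinics of 50 against three UI clinics of 5 (ICC 0.05) gave 8.0%, against 5.6% for the corrected chi-square. That case is extreme, since allocation was balanced on volume, but a strategy that raises uptake could produce unequal later-step denominators.

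**Conclusion.** The concern holds. The stated test does not match the randomised unit, and its p-values cannot be read at the 5% level. The direction follows from any positive ICC, which the plan's own description makes likely. The amount depends on clinic size and ICC, neither of which is reported. Under the assumptions above, the true error runs from no inflation (corrected test, small clinics, ICC near zero) to more than half (50 per clinic, ICC 0.20), with 12% to 33% uncorrected at 30 per clinic and ICC 0.02 to 0.10. This must be fixed because it bears on the study's only randomised inference.

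**What to change.** - For each retention step, compute one proportion per clinic and compare the four AI with the three UI clinics by a t-test on 5 df. Report the difference with its 95% CI and list the results by clinic.
- Treat the AI versus UI comparisons of questionnaires and text frequencies in the same way, using clinic means or proportions. Summarise facilitation dose by clinic too.
- Report denominators per clinic, and warn the reader where they differ strongly between arms.
- State which allocations set randomisation allowed. If a permutation test is added, run it over those allocations only and give its smallest attainable p.
- If the patient-level tests are kept instead, label them descriptive, show results by clinic and drop the p < 0.05 claim. For a study of this size that may be the more natural choice.

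The cost is revised wording and a short re-analysis of data already collected. The drawback is low power: only differences of roughly 30 to 47 points would be detected reliably at 30 per clinic and ICC 0.02 to 0.10. If setting drives much of the clinic variation and was balanced, the t-test is also conservative (1.4% to 4.0% in the simulations). Seven clinics impose that limit, and a patient-level test hides it without removing it.
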